5.4.2 Additional SAS outputs

For the below mentioned analyses, additional (raw) SAS outputs resulted from SAS/STAT procedures or statistical derivations will be presented and used for CSR Appendix 16.1.9:

- Effect Size and 80% Confidence Intervals for APCC score, RBANS Total, RBANS Index scores
- Time to event (TTE) analyses:
 - Time to first confirmed diagnosis of MCI due to AD or Dementia due to AD-SAF
 - Time to first change in diagnosis classification-SAF
 - Time to first change in diagnosis classification when participants are on treatment-SAF

- Time to first change in diagnosis classification when participants are on treatment-mSAF
- Time to first decrease in RBANS Total \geq 14 points when participants are on treatment-SAF
- Baseline comparability

Further details for these additional SAS outputs will be described in the programming notes of the respective shells in the TFL shells Section 16.1.9.

5.5 Rule of exclusion criteria of analysis sets

The important protocol deviations are defined in below [Table 5-4](#) with deviation ID, deviation code and it's corresponding text description.

Rule of exclusion criteria from analysis sets due to important protocol deviations (if any) will be included prior to database lock in a separate document in CREDI.

The Non-PD criteria for exclusion from analysis sets is explained in below [Table 5-5](#).

Table 5-4 Deviation codes description

Deviation code	Text description	Deviation ID
1	SELECTION CRITERIA NOT MET	INCLXX EXCLXX
2	PARTICIPANT NOT WITHDRAWN AS PER PROTOCOL	WITHXX
4	TREATMENT DEVIATION	TRTXX
5	PROHIBITED CONCOMITANT MEDICATION	COMDXX
998	OTHER	OTHXX

Table 5.5 Participant Classification

Analysis Set	PD ID that cause patients to be excluded	Non-PD criteria that cause patients to be excluded
Screened Set	NA	Not having informed consent; Not having screening epoch disposition page
RAS	NA	Not randomized
SAF	NA	No double-blind study drug taken

5.6 Notable and abnormality criteria

Table 5-6 Clinically notable criteria for vital signs

Vital Sign Variable	Notable Criteria
Pulse (beats/min)	> 120bpm or Increase of ≥ 15 bpm from baseline or < 50bpm or Decrease of ≥ 15 bpm from baseline
Systolic BP (mmHg)	>180 mm Hg or Increase of ≥ 20 mm Hg from baseline Or < 90 mm Hg or Decrease of ≥ 20 mm Hg from baseline
Diastolic BP (mmHg)	> 105 mmHg or Increase of ≥ 15 mm Hg from baseline Or < 50 mmHg or Decrease of ≥ 15 mm Hg from baseline
Body weight (kg)	Decrease $\geq 7\%$ from baseline weight Increase $\geq 7\%$ from baseline weight

Table 5-7 Clinically notable criteria for selected hematology tests

Laboratory parameter	SI units		US or other units	
	Lower bound	Upper bound	Lower bound	Upper bound
Hemoglobin	70 (g/L)	200 (g/L)	7 (g/dL)	20 (g/dL)
White Cell count	2 ($\times 10^9/L$)	30 ($\times 10^9/L$)	2 ($\times 10^3/uL$)	30 ($\times 10^3/uL$)

Laboratory parameter	SI units		US or other units	
	Lower bound	Upper bound	Lower bound	Upper bound
Platelets	50 (x10 ⁹ /L)	1000 (x10 ⁹ /L)	50 (x10 ³ /uL)	1000 x10 ³ /uL)

[figure not shown]
Table 5-8 Clinically notable criteria for selected blood chemistry tests

Laboratory parameter	SI units		US or other units	
	Lower bound	Upper bound	Lower bound	Upper bound
Sodium	125 (mmol/L)	155 (mmol/L)	125 (mmol/L)	155 (mmol/L)
Potassium	3 (mmol/L)	6 (mmol/L)	3 (mmol/L)	6 (mmol/L)
Calcium	1.5 (mmol/L)	3 (mmol/L)	6 (mg/dL)	12 (mg/dL)
Magnesium	0.4 (mmol/L)	1.2 (mmol/L)	1 (mg/dL)	3 (mg/dL)
Bilirubin (Total)	-	41 (umol/L)	-	2.4 (mg/dL)
AST	-	> 3×ULN	-	> 3×ULN
ALT	-	> 3×ULN	-	> 3×ULN
Alkaline Phosphatase (Male)	-	> 2×ULN	-	> 2×ULN
Alkaline Phosphatase (Female)	-	> 2×ULN	-	> 2×ULN
Creatinine	-	increase 25 – 49% compared to baseline increase ≥ 50% compared to baseline	-	increase 25 – 49% compared to baseline increase ≥ 50% compared to baseline

Table 5-9 ECG Abnormality Ranges

ECG Parameter	Abnormality Flags
	Absolute
PR interval	> 250 msec
QRS Interval	> 140 msec
QTcF Interval (Fridericia's correction)	>= 500 msec (All) >= 450 msec (Male) >= 470 msec (Female)

ECG Parameter	Abnormality Flags
	Absolute
QT change from baseline	>60 msec

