9.5.2 Safety variables

All safety analyses will be carried out using the SAF. Descriptive summary tables will be provided by treatment for AEs, safety MRI and other safety parameters.

AEs, SAEs and Death

The number (and proportion) of participants with treatment-emergent AEs (events that started after the first dose of study medication or events present prior to the start of double-blind treatment but increased in severity based on preferred term) will be summarized in the following ways:

- by treatment, primary system organ class, and preferred term
- by treatment, primary system organ class, preferred term, and maximum severity
- by treatment, Standardized MedDRA Query (SMQ), and preferred term

Separate summaries will be provided for SAEs, death, and study medication related AEs, AEs leading to discontinuation and AEs leading to dose adjustment.

Laboratory data

Summary statistics of change from baseline laboratory results will be provided over time by treatment arm. These descriptive summaries will be presented by laboratory test category, visit, and treatment arm.

Shift tables will also be provided in which the normal laboratory ranges will be used to evaluate whether a particular laboratory test value is normal, low, or high for each visit relative to whether or not the baseline value is normal, low, or high. The shift from baseline to the most extreme post-baseline value will also be summarized. These summaries will be presented by laboratory test category, treatment and time (if applicable).

The number and percentage of participants with clinically notable laboratory results after baseline will be presented. The most extreme post-dose value is considered. Only participants with laboratory results at baseline and post-baseline from the central laboratory are included in the tabulations.

The number and percentage of participants with predefined liver enzyme abnormalities occurring during the study will be summarized by treatment arm.

Vital signs

Summary statistics of change from baseline values will be presented by vital sign parameter and treatment arm. Number and percentage of participants with clinically notable vital sign changes from baseline will be tabulated by treatment arm.

[figure not shown]
Electrocardiogram (ECG)

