13.1 Clinically notable test values and vital signs

13.1.1 Vital signs

Table 13-1 Clinically notable vital signs

Variable	Change relative to baseline		
Heart Rate	> 120 bpm < 50 bpm	and an and a	increase of \geq 15 bpm decrease of \geq 15 bpm
Systolic BP	> 180 mm Hg < 90 mm Hg	and an and a	increase of \geq 20 mm Hg decrease of \geq 20 mm Hg
Diastolic BP	> 105 mm Hg < 50 mm Hg	and an and a	increase of \geq 15 mm Hg decrease of \geq 15 mm Hg
Weight			change of \geq +/- 7%

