2.5.4 Statistical hypothesis, model, and method of analysis

Except from the primary objective on the TTE endpoint, the other primary objective (for APCC) aimed to evaluate effects of CNP520 versus Placebo by comparing changes from baseline to Month 60. Due to the early termination of CNP520, no data have been collected at Month 60. Only very few participants have provided data on active treatment with CNP520 beyond one year of follow-up. Hence, the originally planned inferential and model based statistical analyses cannot be performed and are no longer applicable.

Time to event (MCI due to AD or dementia due to AD), Time to first change in diagnosis classification and Time to first decrease in RBANS Total of ≥ 14 points

Tables

Time to Event analysis using Kaplan Meier approach will be presented for time to MCI due to AD or Dementia due to AD (events as per protocol) and for time to first change in diagnosis classification (this is an event regardless of confirmation and adjudication) from cognitively unimpaired by the investigator. Analysis of time to first change in diagnosis classification will also be performed for participants on treatment. In addition, analysis of time to first decrease in RBANS Total Score of ≥ 14 points will be performed for participants on treatment (for on treatment definition, refer [Section 2.1.1](#)). The Kaplan-Meier estimates of the cumulative event rate for each treatment group will be summarized and plotted. To calculate the proportion of participants with events, number of participants at risk will be used as the denominator. "Participant at risk" at a specific time point is defined as the number of participants in the study without an event at up to that time point.

These analyses will only be performed if there are at least five such events.

In addition, the number and percentage of the additional situations ([Section 2.5.3](#)) defined events overall (not by visit) will be summarized by treatment group.

APCC score

Tables

The APCC test score and the seven components (listed above in [Section 2.5.3](#)) will be summarized on the SAF.

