2.8.4 Other safety data

2.8.4.1 ECG and cardiac imaging data

12-lead ECGs will be performed at screening and throughout the study in supine position. The ECG values will be interpreted and analyzed centrally. The QT intervals will be corrected according to the formula by Fridericia:

Fridericia's formula: $QTcF = QT/RR^{1/3}$

Tables

The number and percentage of participants with newly occurring or worsening clinically notable ECG abnormalities at any time post-baseline visit will be summarized for all parameters as specified in [Appendix 5.6](#).

Figures

Box plots over time will be presented by ECG parameter and treatment group.

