2.8.4.2 Vital signs

Tables

Parameters to be summarized are the following:

- Change from baseline in body weight will be summarized by visit including last assessment on treatment and last assessment off treatment.
- Vital signs: clinically notable changes (Body weight change will also be split by weight loss and weight gain).

The number and percentage of participants with clinically notable vital signs abnormalities at any time post-baseline visit will be summarized. The criteria of clinically notable vital signs are provided in [Appendix 5.6](#).

Clinically notable weight changes of participants will be further investigated with the following summaries:

Frequency table will be presented for clinically notable weight changes (decrease/increase from baseline $\geq 7\%$ from baseline weight) during the treatment phase, by baseline weight categories (<55 kg, 55 - <70 kg, 70 - <84 kg, ≥ 84 kg) and by gender (Male, Female)

Participant demographics and other baseline characteristics with clinically notable weight decrease (loss) will be summarized.

Figures

For the following parameters, box-plots by visit will be created: Heart Rate, Systolic BP, Diastolic BP, body weight.

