- 30% drop-out rate over five years,
- Target power of 80%,
- $\alpha = 1\%$, two-sided test.

The sample size of $n = 800$ participants in the selected CNP520 dose arm and placebo, respectively, is sufficient to detect an effect size of 0.20 with 80% power. Results from simulations indicate that using a longitudinal model and adjusting for prognostic factors will increase power to detect an effect size of 0.20.

Power calculations for APCC using the two-sided t-test have been performed with nQuery Advisor 7.0.

Overall power

The overall power to detect a true treatment effect in at least one of the two endpoints is higher as compared to the power for the single endpoints. The difference in power between the dual and single endpoints is largest when the endpoints are independent and will be small when the endpoints are strongly positively correlated.

4 Change to protocol specified analyses

SAF definition (defined in [Section 2.2](#)) is different from the protocol defined SAF definition.

An additional analysis set, mSAF, has been defined.

The following analysis were defined in the protocol but will not be performed due to early termination of the study:

- Primary analysis for both the primary endpoints
- Sensitivity to the primary analysis
- Supportive analysis to primary endpoints
- MMRM analysis to key secondary endpoint
- MMRM analysis to secondary efficacy endpoints

■ [REDACTED]

The following analysis were not defined in the protocol but will be added:

- All the efficacy analysis (except worsening in cognition and reversibility) will be performed on the SAF
- Worsening in cognition and reversibility as efficacy analysis using mSAF

5 Appendix

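### SAP Table 5-6 joins limit and change by 'or' where Protocol Table 13-1 uses 'and', without declaring it, so the notable vital-sign table mostly counts ordinary fluctuation

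*SAP*

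**What the plan says.** Protocol Appendix 1, section 13.1.1 ("Table 13-1 Clinically notable vital signs"), gives limits for heart rate, systolic and diastolic pressure. In the systolic row they are "> 180 mm Hg < 90 mm Hg". The middle column of the table joins each limit by 'and' to a minimum rise (high side) or fall (low side) from baseline. Protocol 9.5.2 then plans this output: "Number and percentage of participants with clinically notable vital sign changes from baseline will be tabulated by treatment arm".

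SAP Appendix 5.6, Table 5-6, carries the same limits and the same changes under the same label, but joins them by 'or' on both sides for pulse, systolic and diastolic pressure. The systolic high side is ">180 mm Hg or Increase of ≥ 20 mm Hg from baseline". SAP 2.8.4.2 applies the table as follows: "The number and percentage of participants with clinically notable vital signs abnormalities at any time post-baseline visit will be summarized". It does not require the value to be new or worse than at baseline. The ECG section next to it does, counting "newly occurring or worsening clinically notable ECG abnormalities at any time post-baseline visit", and SAP 2.8.3 does the same for laboratory values.

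SAP Section 4 lists departures from the protocol. It records that the safety set "is different from the protocol defined SAF definition". Its visible text does not mention the vital-sign rule, and neither does the visible part of the SAP change log.

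**The concern.** The protocol's rule picks out people who end up at an extreme and who moved to get there. The SAP's rule also admits two other groups: people who moved by the stated amount but stayed well inside the limits, and people who sat beyond a limit from the start and never moved. The second group has no change from baseline at all, although Protocol 9.5.2 describes the output as changes from baseline.

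A reader comparing the study report with the protocol would take the counts as protocol-defined extremes. A small real excess of extremes in one arm would sit on a large background common to all arms. Little else in the plan covers this. SAP 2.8.4.2 keeps change-from-baseline tables for body weight only, so the notable-value table is the only pulse and blood pressure table named there. The box-plots by visit remain, but they give no participant counts.

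**Working it through.** **Inputs from the documents.** The limits U and L and the change c are the same in both tables.

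| Parameter | U | L | c |
|---|---|---|---|
| Pulse (bpm) | 120 | 50 | 15 |
| Systolic (mm Hg) | 180 | 90 | 20 |
| Diastolic (mm Hg) | 105 | 50 | 15 |

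**The two rules**, for baseline b and post-baseline value y:

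- Protocol: (y > U and y − b ≥ c) or (y < L and b − y ≥ c).
- SAP: y > U, or y − b ≥ c, or y < L, or b − y ≥ c.

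Any value that meets the first rule meets the second; the reverse fails.

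| Case | Protocol | SAP |
|---|---|---|
| Systolic 118 → 138 (rise 20, not above 180) | no | yes |
| Systolic 182 → 182 (change 0) | no | yes |
| Pulse 49 → 49 (change 0) | no | yes |
| Diastolic 70 → 85 (rise 15, not above 105) | no | yes |
| Systolic 120 → 185 (rise 65, above 180) | yes | yes |

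**Size.** The plan gives no expected rate, so there is no figure of its own to reproduce. The means and SDs below are assumptions. Each reading is a normal person-level mean plus independent normal visit noise with SD s, and there is no drug effect.

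The change-only part at one visit has a closed form. The difference y − b has SD s√2. For systolic with s = 10 that is 14.14, and P(|y − b| ≥ 20) = 2[1 − Φ(20/14.14)] = 2[1 − Φ(1.414)] ≈ 15.7%. Values beyond a limit without the change bring the total to about 16%.

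Repeated visits need numerical integration over the person mean and one noisy baseline. One to four visits correspond to the Week 13, 26, 39 and 52 windows of SAP Table 5-14. SAP 2.5.4 supports stopping there: "Only very few participants have provided data on active treatment with CNP520 beyond one year of follow-up". Systolic, mean 130, between-person SD 12, s = 10 (range for s = 8 to 12):

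| Visits | 'or' | 'and' |
|---|---|---|
| 1 | 16% (8–24) | 0.3% (0.1–0.6) |
| 2 | 27% (14–40) | 0.5% (0.2–1.2) |
| 3 | 36% (19–51) | 0.8% (0.2–1.8) |
| 4 | 43% (23–59) | 1.0% (0.3–2.3) |

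Simulating 400,000 participants agrees with the integration for 'or': 16.0% against 16.2% at one visit and 42.7% against 42.9% at four. At s = 6, 'or' falls to 2% at one visit and 7% at four.

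The other two parameters, with s = 6 (range 5 to 7):

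| Parameter (mean, between-person SD) | Visits | 'or' | 'and' |
|---|---|---|---|
| Pulse (67, 8) | 1 | 11% (7–17) | 0.8% (0.3–1.4) |
| Pulse (67, 8) | 4 | 31% (18–43) | 2.7% (1.1–5.0) |
| Diastolic (78, 7) | 1 | 8% (4–13) | 0.1% (0.03–0.3) |
| Diastolic (78, 7) | 4 | 23% (11–36) | 0.4% (0.1–1.1) |

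The share of SAP flags that fail the protocol's rule at four visits is 1 − 1.0/43 ≈ 98% (systolic), 1 − 2.7/31 ≈ 91% (pulse) and 1 − 0.4/23 ≈ 98% (diastolic). Over the stated ranges and all visit counts it is 96–99%, 89–95% and 97–99%.

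**Effect on a real signal** (systolic, three visits, s = 10):

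| Scenario in one arm | 'and' | 'or' |
|---|---|---|
| No effect | 0.8% | 36% |
| 2% of participants rise by 50 mm Hg | 2.2% | 37% |
| Whole arm rises by 5 mm Hg | 0.6% | 39% |

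**The case against.** The best defence has four parts.

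- **No safety information is lost.** 'Or' drops no case that 'and' would catch, and it responds better to a general shift (36% to 39%, while 'and' does not rise). In the 2% / 50 mm Hg case the absolute excess is about the same under both rules: 2.20 − 0.77 ≈ 1.4 points under 'and' and 37.1 − 35.8 = 1.3 under 'or'. This is correct. What is lost is visibility: 'and' goes to 2.2/0.8 ≈ 2.8 times its background, 'or' to 37/36 ≈ 1.03 times.
- **Stable values may not be meant to count.** A bullet in SAP 2.8.4.2 describes the output as notable changes. But the same section takes its criteria from Appendix 5.6, where a value beyond the limit qualifies alone, so the bullet adds a conflict without settling it. This group is small for blood pressure. Under similar assumptions with wider within-person SDs, over three visits, values beyond a limit without the change occur in 0.4–1.3% (systolic), 0.5–1.9% (diastolic) and 4.2–8.3% (pulse).
- **The table shells might split the conditions into separate rows.** They are not available. Nothing in the SAP says that they restore the joint condition.
- **The stakes are modest.** The trial stopped early because of cognitive worsening, the report is abbreviated, and this is a descriptive table. That stands, and it limits the severity.

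The search for a declaration covers visible text only: one bullet in SAP Section 4 is blacked out and earlier log pages were removed. The bullet sits among analyses that will not be performed, an unlikely place for a changed definition.

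**Conclusion.** The concern holds. The two tables use the same label and numbers but different logic, and the visible SAP does not declare the change. The SAP as written reports a different quantity from the one the protocol promises. That conclusion, and the fact that the SAP's count can only be equal or larger, need no assumptions.

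The percentages do rest on assumed means and SDs. Across the main ranges roughly nine in ten or more flags would fail the protocol's rule, but the absolute 'or' rate varies widely: for systolic pressure at four visits it runs from 7% (within-person SD 6) to 59% (SD 12). The change favours no arm and leaves type I error, power, the box-plots and the 7% weight criterion untouched. It should be corrected, but it does not threaten the trial's main conclusions.

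**What to change.** Reconcile SAP Table 5-6 with Protocol Table 13-1 so that the output reports the protocol's limit-and-change count for pulse, systolic and diastolic pressure. If limit-only or change-only counts are also wanted, give them separately labelled rows. If 'or' was intended, declare and justify it in SAP Section 4, and state in SAP 2.8.4.2 whether only values that are new or worse than at baseline count. This concerns the reported count only; it takes no view on which limits are clinically right or on any treatment decision.

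The cost is small: three cells of Table 5-6, one line in Section 4, and a rerun of one descriptive safety table. The SAP log already contains numbered addenda made after database lock, so the route exists.

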6.4.5 Electrocardiogram (ECG)

ECGs will be centrally evaluated. Full details of all procedures relating to the ECG collection and reporting will be contained in the technical manual, which is provided to the site by the centralized ECG vendor.

[figure not shown]
Twelve-lead standard ECGs will be recorded in triplicate (one minute apart) after participants have been resting in the supine position for at least 10 minutes. The ECGs should be scheduled approximately 2.5 hours post CNP520 drug administration on site ([Section 5.5.4](#)). If the LDR is 50 mg once weekly and the dosing day corresponds to the visit day then the scheduled is maintained otherwise, the ECG should be taken preferably at the same time of the day than earlier visits.

[figure not shown]
The Fridericia QT correction formula (QTcF) should be used for clinical decisions.

Electrocardiograms will be obtained as designated in the [Table 6-1](#), if applicable.

The ECG readings will be sent automatically to the centralized ECG vendor. Findings at screening, considered as clinically significant and meeting alert values, in the opinion of the investigator, must be discussed with the Novartis Medical Monitor before administration of investigational treatment.

Each ECG tracing must be labeled with study number, participant initials, participant number, date and time, and filed in the study site source documents. For any ECGs with participant safety concerns, two additional ECGs must be performed to confirm the safety finding and copies forwarded to the central ECG laboratory for assessment.

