13.1.2 Clinically notable ECG and laboratory values

Abnormal ECG values will be specified in the manual from the centralized ECG vendor, with specific telephone alert values and panic alert values.

Figure 13-1 Abnormal ECG measurements leading to exclusion alerts

Category	Values leading to exclusion alerts
HR_MN	< 40 or > 120
Mean QRS interval	> 140 ms
Mean QTcF interval	> 500 ms

Abnormal laboratory values will be specified in the manual from the central laboratory with specific telephone alert values and panic alert values.

The Novartis Medical Monitor will be notified by email and fax at the same time as the investigator for all types of alerts.

Discontinuation of study medication, for individual participant, is required in case of clinically significant ECG or laboratory findings considered to be suspected to be related to study medication, as judged by Investigator or the DMC, respectively.

Table 13-2 Abnormal laboratory values leading to participant exclusion

Organ	Laboratory value	Limits
Liver	ALT or AST	> 5 × ULN
	ALP	> 2 × ULN (in the absence of known bone pathology)
	TBL	> 2 × ULN (in the absence of known Gilbert syndrome)
	ALT or AST and INR	> 3 × ULN and > 1.5

Organ	Laboratory value	Limits
Renal	Estimated glomerular filtration rate (GFR)	<30mL/min (calculated using the Cockcroft-Gault formula)
Blood (chemistry)	Calcium (mg/dL)	<7.0; >12.5
	Phosphorus (mg/dL)	<2.0
	Sodium (mmol/L)	<125; >155
	Potassium (mmol/L)	<3.0; >6.0
Blood (Hematology)	Magnesium (mg/dL)	>3.0
	HGB (g/dL)	<8.0; ≥19.0
	WBC (GI/L)	<2.0; ≥13.0
	Platelets (GI/L)	<50; ≥700

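### SAP Table 5-9 names QTcF for the absolute limits but only QT for the 60 ms change limit; taken literally, that flag depends on heart rate

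*SAP*

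**What the plan says.** SAP section 5.6, Table 5-9, lists the ECG abnormality ranges. The QT limits on absolute values (500 ms for all, 450 ms for men, 470 ms for women) belong to a row labelled "QTcF Interval (Fridericia's correction". The change limit, above 60 ms, belongs to a separate row labelled "QT change from baseline". No row gives a change limit for QTcF.

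The table feeds a planned output. SAP 2.8.4.1 plans a tabulation of counts and percentages, described in these words: "newly occurring or worsening clinically notable ECG abnormalities at any time post-baseline visit will be summarized for all parameters as specified in". The reference is to the SAP section that holds Table 5-9. The same section on ECG data states: "The QT intervals will be corrected according to the formula by Fridericia", and gives the formula.

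The protocol points the same way. Section 6.4.5 says: "The Fridericia QT correction formula (QTcF) should be used for clinical decisions". The exclusion alert in section 13.1.2 is set on "Mean QTcF interval". Protocol section 9.5.2 plans a summary of notable ECG abnormalities but sets no threshold for QT change, so it does not settle what the SAP row means.

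**The concern.** Two QT rows stand next to each other. One names the correction and the other does not, so the natural reading of the second is raw QT. Raw QT lengthens when the heart slows and shortens when it speeds up, with no change in repolarisation.

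A change criterion on raw QT can therefore err in two ways. It can count a participant whose heart rate merely fell. It can also miss a participant whose corrected QT rose by more than 60 ms while the rate went up. The second error matters more, because a change criterion is there to catch a large within-person rise that stays below the absolute limits.

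**Working it through.** The plan states no figure to reproduce, so the check applies the SAP's own formula to the row as labelled.

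**Inputs**
- Change threshold: above 60 ms (SAP Table 5-9).
- Absolute QTcF limits: 450 ms (men), 470 ms (women), 500 ms (all) (SAP Table 5-9).
- "Fridericia's formula" (SAP 2.8.4.1): QTcF = QT / RR^(1/3). With RR = 60/HR in seconds, this inverts to QT = QTcF × (60/HR)^(1/3).
- QTcF and heart-rate values: **assumptions**, because the documents give none. The range used is QTcF 375 to 445 ms and heart rate 45 to 90 bpm.

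**Slowing alone, with QTcF unchanged**

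At QTcF 420 ms:
- HR 90: 420 × (60/90)^(1/3) = 366.9 ms
- HR 80: 420 × (60/80)^(1/3) = 381.6 ms
- HR 55: 420 × (60/55)^(1/3) = 432.4 ms

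A fall from 90 to 55 bpm gives a QT change of about +65 ms, which is flagged. A fall from 80 to 55 bpm gives 432.4 − 381.6 = +50.8 ms, which is not.

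Other combinations, QTcF constant:

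| QTcF (ms) | HR 75 to 60 | HR 75 to 50 | HR 80 to 50 | HR 70 to 45 |
|---|---|---|---|---|
| 380 | +27.2 | +51.0 | +58.6 | +57.3 |
| 400 | +28.7 | +53.7 | +61.6 | +60.3 |
| 420 | +30.1 | +56.4 | +64.7 | +63.3 |
| 440 | +31.5 | +59.1 | +67.8 | +66.3 |

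For QTcF between 380 and 440 ms, a false flag needs the rate to fall below about 49.5 to 52.6 bpm from 80, or below about 46.8 to 49.7 bpm from 75. That is a fall of roughly 25 to 30 bpm.

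**True prolongation with a faster rate**

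Take QTcF rising from 380 to 445 ms, a true change of +65 ms, with heart rate going from 60 to 65 bpm:
- Baseline QT: 380 × (60/60)^(1/3) = 380.0 ms
- Follow-up QT: 445 × (60/65)^(1/3) = 433.3 ms
- Change in QT: +53.3 ms, not flagged

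| QTcF change | HR 60 to 65 | HR 60 to 70 | HR 60 to 80 |
|---|---|---|---|
| 380 to 445 (+65) | +53.3 | +42.7 | +24.3 |
| 375 to 445 (+70) | +58.3 | +47.7 | +29.3 |

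None of these crosses 60 ms. The final QTcF of 445 ms is also below 450, 470 and 500 ms, so no QT row of the table catches them.

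**With the row on QTcF.** In every constant-QTcF case the change is 0 ms and nothing is flagged. The rises from 380 to 445 ms (+65) and from 375 to 445 ms (+70) are both flagged.

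**The case against.** The strongest reply is that the row never says uncorrected. SAP 2.8.4.1, which calls this table, states without exception that QT intervals are corrected, so QT change placed just below a QTcF row may simply be shorthand. The protocol is itself loose with the terms: exclusion criterion 17 speaks of QTc and of a prolonged QT interval without naming Fridericia. SAP section 5.4 places the SAS code in the TFL shells, which are not available here. This stands. A reader might infer that the wrong variable was analysed, or that every other QT statement in the documents uses QTcF; the documents support neither. The supportable claim is that the label, as written, names the wrong measure or leaves the measure unclear.

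A second reply is that the row is not the only QT safeguard. The absolute QTcF limits are also judged as newly occurring or worsening, box plots over time are planned, and ECGs are read centrally with vendor alerts. A false flag needs a large fall in rate in participants who have rested supine for at least 10 minutes before triplicate recordings. This stands too, though a rise of only 5 bpm is enough to hide the examples above.

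A reader might also connect this row with Amendment 1, which allowed drugs associated with Torsades de Pointes, and infer a serious safety gap. The documents do not support that. The amendment's stated reason is a pooled analysis that found no relevant QT prolongation, and Protocol 3.6 reports no QTcF prolongation in it.

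**Conclusion.** The point holds as a defect in one row of one table. Read literally, Table 5-9 applies its 60 ms change limit to a heart-rate-dependent measure, in conflict with the correction stated in SAP 2.8.4.1. Read as shorthand, the label still needs correcting, because neither a programmer nor a reader of the output can tell from the table which measure was meant.

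The sizes depend on assumed QTcF and heart-rate values and show what can happen, not how often. Hidden cases escape every QT row only if the final QTcF stays below the applicable absolute limit.

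The consequence is minor: one descriptive outlier count in an abbreviated report, with no bearing on efficacy, alpha or sample size. A reader might infer a biased comparison between arms. Nothing in the documents shows that, since rate-related noise would affect placebo as well.

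**What to change.** Relabel and program the Table 5-9 row as *QTcF change from baseline, above 60 msec*, leaving the threshold as it is. If uncorrected QT was intended, say so in the table and add a separate row for QTcF change.

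The cost is one label and one variable in one table program; QTcF is already needed for the absolute limits. The SAP's change history shows addenda issued after database lock, so a short clarifying note and a rerun of that one table would be enough. If the existing program already uses QTcF, only the label changes.
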